assessments will be used to determine whether participants in STEP-KOA need to progress to more intensive steps. The primary outcome point (Aim 1) will be at nine months. In addition, Aim 2 will examine whether any effects are maintained in the STEP-KOA group in the six months following the intervention period (15 months post-randomization). A six-month follow-up period is meaningful for assessing maintenance in the context of physical activity trials among patients with OA^{56,57}, and it is feasible to complete within the study period. Following completion of 9-month assessments, participants assigned to the AE control group will receive access to the internet-based exercise training program, along with the Step 2 exercise counseling calls. (Therefore, the AE group will not complete 15-month assessments, as Aim 2 will now include the STEP-KOA group only.) We chose to provide treatment to the AE group after nine months because 15 months was deemed to be an overly long waiting period in the context of a symptomatic condition; this not only raises ethical concerns but scientific ones, since a long wait list period would increase the likelihood of participants seeking physical therapy outside the context of the study during that time frame. We acknowledge that this strategy means that we will not be able to test between-group differences at a longer-term, 15-month follow-up period. However, we will still gain valuable information by assessing whether any changes observed within the STEP-KOA group are maintained over time (9-months to 15-months) and whether this may differ among participants exposed to the different Steps of the program. All participants will continue other usual medical care for OA during the full study period, as recommended by their providers.

2.0 Study Sites. This study will be conducted in two sites in the VA Mid-Atlantic Health Care Network (VISN 6), Durham, NC and Greenville, NC, to enhance generalizability. The Durham VAMC is more urban, and the Greenville VAMC (also known as the Greenville Health Care Center) is located in a more rural and coastal region. Participants will be able to select a different study site from the one originally assigned if their location is closer to the other site.

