7.10 Knee OA and Related Care During Study Period. We will assess use of treatments for knee OA at baseline and follow-up assessments, including pain medications, topical creams, knee braces, joint injections, and assistive devices. We will assess this via self-report, as well as using VA medical records to identify receipt of physical therapy for knee OA, participation in MOVE!, and prescription pain medication use. We may also examine Fee Basis files to more comprehensively assess care received outside the VA. We will not exclude participants who have new OA treatments during the study period. However, it is important to evaluate whether there are differences in these treatments across study groups. If differences are observed, we will conduct two types of sensitivity analyses: a.) participants who received specific treatments will be excluded from analyses, b.) the specific treatment (e.g., new MOVE! participation) will be included as a covariate in statistical models. In addition, if we find that $\geq 20\%$ of participants have a change in any given type of treatment, we will conduct a sensitivity analysis that removes these participants. Because of the drastic improvements typically associated with joint replacement surgery, participants having this surgery during the study period will not be included in analyses of WOMAC scores. However, since receipt of total joint replacement is also an important OA outcome, we will compare the proportions of participants in each study group who receive this surgery during the study period.

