8.0 Data Analyses

8.1. General Considerations. Primary study analyses will be conducted on an intent-to-treat basis, with participants analyzed in the group to which they were assigned. Additional exploratory analyses focusing on more restrictive analytic cohorts (e.g., per protocol analysis) will be considered, to provide additional information about the impact of magnitude of exposure to the intervention. The main conclusions drawn from this trial will be based on the pre-specified primary and secondary hypotheses outlined below and will be tested with two-sided p-values at the standard 0.05 level unless noted otherwise. Statistical analyses will be performed using SAS for Windows (Version 9.2: SAS Institute, Cary, NC) and R (<http://www.R-project.org/>).

8.2. Primary Analysis (Specific Aim 1). The main study outcome, WOMAC, is a continuous measure collected at baseline, 3, 6, 9 and 15 months (STEP-KOA group only). For the primary hypothesis we will examine STEP-KOA effects at the 9-month assessment. We will use a linear mixed model (LMM) that accounts for the correlation between a participant's repeated outcome measurements over time. We will apply an unstructured covariance matrix to take into account the within-patient correlation between repeated measures. The fixed-effect portion of the model will have the form: $Y_{it} = \beta_0 + \beta_1 3\text{month} + \beta_2 6\text{month} + \beta_3 9\text{month} + \beta_4 \text{STEP-KOA} * 3\text{month} + \beta_5 \text{STEP-KOA} * 6\text{month} + \beta_6 \text{STEP-KOA} * 9\text{month}$, where Y_{it} is the WOMAC score for subject i at $t=0, 3, 6, \text{ and } 9\text{months}$. We will estimate the parameters in the model and set up contrasts for tests of hypotheses using the SAS procedure MIXED (Cary, NC). Specifically, for Hypothesis 1, we will test for a difference in mean WOMAC scores between the STEP-KOA and AE groups at 9-months by testing that $\beta_6=0$.

Time is coded in the model to fit a constrained longitudinal data model (cLDA), in which baseline WOMAC score is modeled as a dependent variable in conjunction with the constraint of a common baseline mean across treatment arms⁸³. For improvement in precision, the model will be adjusted for stratification variables⁸⁴.

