8.3. Secondary Analyses. Since the secondary outcomes, 30 second chair stand and 40 meter fast-paced walk, are continuous, longitudinally collected measures, we will use similar modeling procedures as those described above for WOMAC scores to assess between-group differences at 9-month follow-up. We will also examine Poisson or negative-binomial mixed models as a sensitivity analysis as these outcomes (particularly chair stands) can be skewed and assumption of a normal distribution may not be reasonable.

For Specific Aim 2, to examine the maintenance effects of STEP-KOA at the 15-month follow-up, we will add the 15-month outcomes and the 15-month time-point to the fixed effect portion of the model. As we will only be estimating the maintenance effects for participants randomized to the STEP-KOA arm, we will drop the treatment by time variables from the fixed effects. We will set up contrasts of model parameters to estimate the difference and associated 95% confidence intervals in outcomes between the 9-month and 15-month time points. Models will also be fit to estimate these differences for subgroups defined by the combination of steps received during the STEP-KOA program by adding variables to the fixed effects indicative of the steps received as well as their interactions with time.

For Specific Aim 3, we are interested in understanding the flow of responders and non-responders through the STEP-KOA intervention. Our goal is to determine whether there are patient-level factors, already known or easily determined in routine clinic visits, which could be used by providers (individually or in combination), to guide referral of patients to a Step that is most likely to meet their needs. We will first calculate proportions of responders and non-responders at each time point and describe responder patterns longitudinally. We will also calculate proportions of individuals who meet response criteria in the two-different way described in Section C.5.1. We will then examine characteristics associated with responder status at each time point, using multivariable logistic regression models. In these models, we will first focus on the four *a priori* patient characteristics: age, baseline pain and function, and baseline self-rated health, to avoid spurious statistical findings⁸⁵. Based on clinical experience, we believe these variables have potential to predict response, and they can be assessed easily and quickly, making them practical screening tools.

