8.4. Missing Data. Because the main predictors of interest, intervention arm and patient characteristics, are collected at baseline, we do not anticipate much missing data in these variables. There may be missing values in the follow-up outcome measures due to dropout, death, a missed interim assessment, or item non-response. Our main analysis technique for the primary outcomes, general linear mixed models via maximum likelihood estimation, implicitly accommodates missingness when missingness is due either to treatment, to prior outcome, or to other baseline covariates included in the model, defined as missing at random^{86,87}. If the missing values are related to other measured patient factors, then multiple imputation (MI) provides a framework for incorporating information from these variables, while still preserving a parsimonious main treatment effect model^{88,89}. Depending on the type and scope of missing data, MI will be conducted via the SAS procedure PROC MI or the SAS macro IVEware (<http://www.isr.umich.edu/src/smp/ive/>).

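### Section 7.10 drops whole participants from the WOMAC analyses after joint replacement, so usable pre-surgery scores are lost, and the window for the rule is undefined

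*Combined protocol and SAP*

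**What the plan says.** Section 7.10 sets a general rule for new knee OA care: "We will not exclude participants who have new OA treatments during the study period". For treatments other than surgery, removing participants is reserved for sensitivity analyses. Joint replacement is the one exception: because of the improvement that usually follows it, "participants having this surgery during the study period will not be included in analyses of WOMAC scores". The section also treats the surgery as an outcome: "we will compare the proportions of participants in each study group who receive this surgery during the study period". It does not say at which month the study period ends.

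Section 8.1 states: "Primary study analyses will be conducted on an intent-to-treat basis, with participants analyzed in the group to which they were assigned". It describes more restrictive cohorts as exploratory and does not mention surgery. Section 8.2 specifies a constrained longitudinal mixed model for WOMAC at months 0, 3, 6 and 9, with the test at month 9. Section 8.4 says that this model "implicitly accommodates missingness when missingness is due either to treatment, to prior outcome, or to other baseline covariates included in the model". For Aim 2, section 8.3 will "estimate the difference and associated 95% confidence intervals in outcomes between the 9-month and 15-month time points". Section 1.0 notes that "the AE group will not complete 15-month assessments, as Aim 2 will now include the STEP-KOA group only".

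**The concern.** The rule acts on people, but its reason concerns scores. Surgery can distort only the WOMAC scores recorded after it. A participant operated on in month 7 has unaffected scores at baseline and at months 3 and 6, and a likelihood-based repeated-measures model is designed to use such a partial record. Read literally, section 7.10 discards the whole record because of something that happened after randomisation and that the same section regards as an outcome that may differ by arm.

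The undefined window adds to this. The primary time point is month 9, but STEP-KOA is followed to month 15. If the window runs past month 9, a participant operated on in months 9 to 15 loses a complete set of pre-surgical scores, including the 9-month score that carries the primary contrast. In STEP-KOA, the same score also leaves the Aim 2 comparison of months 9 and 15.

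At stake is the primary analysis set. A programmer working from section 8 and one working from section 7.10 would build different sets, and the plan has no WOMAC analysis that would show what the exclusion did.

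**Working it through.** **Inputs from section 8.5.** SD 17.5; baseline to follow-up correlation 0.4; target difference 5.8; two-sided alpha 0.05; 80% power; 2:1 allocation; 20% attrition; 230 + 115 = 345.

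**The plan's own figure.** The two-sample calculation needs 108 AE participants before adjustment. 108 × (1 − 0.4²) = 108 × 0.84 = 90.7, so 91 AE and 273 in total. 91/0.8 = 113.75, so 114 AE and 342 in total, against 345 stated: reproduced. Completers are 230 × 0.8 = 184 and 115 × 0.8 = 92. The standard error these inputs imply is 17.5 × √0.84 × √(1/184 + 1/92) = 2.05 points.

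**Assumed inputs.** The documents give neither a surgery rate nor the WOMAC gap between participants who do and do not have surgery. I take 3% surgery by month 9 (range 1% to 5%), a constant hazard, so the share still unoperated at month t is (1 − p)^(t/9), and no other missing data.

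**Scores deleted, 9-month window.**
- Excluded: 345 × 0.03 = 10.4 participants (3 to 17 over the range).
- A participant operated on in months 0–3, 3–6 or 6–9 has 1, 2 or 3 earlier scores. The loss is 345 × (1 × 0.01010 + 2 × 0.01000 + 3 × 0.00990) = 20.6 scores (7 to 34).

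**Scores deleted, 15-month window.**
- Surgery by month 15: 1 − 0.97^(15/9) = 4.95%, so 17.1 excluded (6 to 28).
- Operated on after month 9: 17.1 − 10.4 = 6.7 (2 to 11), each with four pre-surgical scores, the 9-month score among them.
- Scores lost up to month 9: 20.6 + 4 × 6.7 = 47.5 (16 to 78).

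**Shift in the 9-month contrast.** Let c be how much worse the excluded participants would score at month 9, without surgery, than their whole arm. Removing a share p moves that arm's mean by c × p/(1 − p), so the contrast moves by c × [p₁/(1 − p₁) − p₀/(1 − p₀)]. If the same gap is present at baseline, the baseline adjustment leaves 1 − 0.4 = 0.6 of this. Take c as 10 to 20 points.
- Common window, equal rates, equal gaps: the bracket is zero, so no expected shift.
- Common 9-month window, 4% v 2%: 0.04167 − 0.02041 = 0.02126, giving 0.21 to 0.43; with the factor 0.6, 0.13 to 0.26.
- Common 15-month window, same hazards: 1 − 0.96^(15/9) = 6.58% and 1 − 0.98^(15/9) = 3.31%. Then 0.07041 − 0.03425 = 0.03616, giving 0.36 to 0.72; with the factor 0.6, 0.22 to 0.43.

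The shift favours the arm with more surgery, because that arm loses more of its worst scorers. The largest value is 0.72/5.8 = 12% of the target and 0.72/2.05 = 35% of the standard error.

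**Simulation check.** The constrained model was fitted by maximum likelihood to 1,000,000 simulated participants per arm. The true difference was −5.8, surgery before month 9 became likelier with a worse last recorded score, and the correlation between follow-ups was assumed to be 0.4 to 0.7. With about 5% surgery in AE and 2% in STEP-KOA, whole-participant exclusion gave −5.68 to −5.62 against −5.78 to −5.82 with full data, a shift of 0.10 to 0.20 towards zero. Keeping pre-surgery scores came within 0.01 of the full-data value. That agreement follows from the set-up: surgery depended only on recorded scores.

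**The case against.** The rule is pre-specified, has a reason and applies to both arms. Section 3.0 excludes people with surgery planned in the next 9 months, so early events should be few, and section 7.10 compares surgery proportions, so an imbalance would be visible. On the assumed 3%, the lost scores are 20.6/1,380 = 1.5% or 47.5/1,380 = 3.4% of the 345 × 4 = 1,380 scheduled to month 9. With a 9-month window, the excluded participants have no usable 9-month score under the proposed handling either. All of this stands, and it is why the effect is probably modest.

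A reader might infer that section 7.10 breaches the intent-to-treat statement. The documents do not support that. Section 8.1 explains the principle as analysis by assigned group, and a specific rule can limit a general one. The proposed handling also sets aside scores because of surgery and targets a no-surgery effect; using every score would be the plain intent-to-treat alternative. What remains is that section 8.1 does not carry the exception, and that the rule removes more than its reason covers.

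A reader might also infer that exclusions would be counted to month 15 in STEP-KOA but only to month 9 in AE. At equal rates that would favour STEP-KOA: 0.0495/0.9505 − 0.03/0.97 = 0.0211, or 0.21 to 0.42 points for the same gaps (0.13 to 0.25 with the factor 0.6). The text does not say this, and one common window is the more natural reading. Section 7.10 says "We will assess use of treatments for knee OA at baseline and follow-up assessments", and AE has no assessment after month 9, but other sources exist. Section 7.11 includes fee-basis OA-related outpatient care, section 11.1 ticks progress notes and discharge summaries (though not operative reports), and the promised comparison of proportions implies capture in both arms.

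**Conclusion.** The concern holds as a should-fix matter about the definition of the primary analysis set. As written, the rule removes whole participants for a post-randomisation event, its window is undefined, section 8.1 does not mention it, and no planned WOMAC analysis retains these participants. Loss of 9-month scores, for Aim 1 and for Aim 2, is conditional: it arises only if the window runs past month 9.

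Any size rests on assumed surgery rates and gaps. The expected shift is nil with a common window, equal rates and equal gaps, and a few tenths of a point under the unequal rates shown. The upper value of 0.72 belongs to a 15-month window, a 20-point gap and no offset from baseline adjustment. It is the top of these scenarios and not a bound. The direction cannot be known in advance.

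**What to change.** - Keep all randomised participants in the WOMAC model, keep every score recorded before surgery, and set only post-surgery scores to missing.
- For Aim 1 and for the comparison of surgery proportions, count surgery from randomisation to the 9-month visit in both arms. For Aim 2, set only post-surgery scores to missing.
- Name joint replacement and its date among the items taken from the existing self-report and record sources in both arms, and cross-reference the handling in section 8.1.
- Report the present full exclusion as a sensitivity analysis and, where post-surgery scores exist, an as-observed analysis as another.
- Reconcile sections 3.0, 7.0 and 7.10. Surgery figures in the exclusion criteria, section 7.0 allows withdrawal when a new problem relates to those criteria, and section 7.10 speaks only of analysis. The documents should state whether participants who have surgery are withdrawn or still assessed.

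The cost is SAP wording, one recorded date and one or two extra model runs; the sample size does not change. The main model would estimate the effect as if surgery had not occurred, which is close to the aim of section 7.10, and would assume post-surgery scores are missing at random given the recorded ones. Bias can remain if surgery follows worsening between visits that no score captured. The as-observed analysis may not be possible if participants are withdrawn.

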7.11 Measures for Cost-Effectiveness Analysis

Intervention Costs. We will use a micro-costing approach to derive labor and equipment costs for the STEP-KOA intervention. Labor costs for Step 1 will include programmer time to maintain the website and phone calls for technical support. Labor costs for the Step 2 intervention will include the time needed to train the exercise counselor and to conduct the telephone calls; this time will include any required pre-call preparation, post-call activities, partial call completions, call attempts and callbacks. Labor costs for Step 3 will involve the therapist's time to complete in-person visits. Hourly wage + fringe benefit rates for personnel will be applied to the labor time to derive total labor costs. The equipment costs for Step 1 include ankle weight and therapy bands, as well as the Apple iPad Air 16GB (encrypted with FIPS 140-2) (Version 9.3.1 (13E238) with Mobile Broadband Access Calling Plan costs for a subset of participants. Equipment costs for Step 3 include any devices recommended by the physical therapist. Adaptations to the existing VET-KOA website for this project will be one-time study-related costs and not included in the intervention cost estimate. Total labor and equipment costs will be divided by the number of patients in the STEP-KOA arm to derive per-patient intervention cost. We note that costs will vary across participants, participants will not all receive the same Steps. We will report this variability but are primarily interested in the average cost per participant.

Patient Resource Utilization and Costs. The intervention may affect primary care and specialist outpatient visits for OA and outpatient pain medication use. To assess VA outpatient visits and VA prescribed pain medication use and costs we will utilize the outpatient extract and pharmacy data extracts from the *DSS Outpatient National Data Extract (NDE)*, and the *DSS NDE SAS Pharmacy Dataset*. Outpatient encounters will be categorized using clinic stop codes of interest, as well as a count of total encounters and total costs of OA-related outpatient care. We will also include fee basis OA-related outpatient care and costs of the same categories because these are of increasing importance to VAMCs.

Effectiveness Measures. We will use two effectiveness measures to calculate cost effectiveness ratios: WOMAC units (described above) and the EuroQoL EQ-5D-5L questionnaire. The EuroQoL health outcome measure (EQ-5D-5L and EQ-VAS) allows us to calculate quality-adjusted life years (QALYs), and it has been used successfully in previous research among patients with arthritis ⁸².

7.12 Participant Feedback on STEP-KOA. We will ask open-ended questions regarding the intervention components. For example, we will ask participants about usability of the VET-KOA website, appropriateness of the number and length of telephone sessions with the exercise counselor, content of PT visits, and ways we can improve the interventions.

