9.0 Economic Evaluation. The overall goal of Specific Aim #4 is to provide the VA with information about the value of the STEP-KOA program, from a cost effectiveness perspective. In addition to informing the VA regarding the overall average cost of STEP-KOA per patient, this evaluation will provide information on how much improvement in outcomes can be achieved for that cost. This information is important for evaluating the potential for downstream implementation of STEP-KOA under various assumptions about scale and scope. We will not evaluate differences in costs or cost effectiveness according to the number of Steps each participant received; rather this will be a simple approach that is consistent with using the VHA perspective and comparing total aggregated costs across the two study arms (STEP-KOA vs. AE) at the 9-month follow-up point. The analysis will begin with descriptive statistics of the cost and effectiveness (utility) data. We will examine each measure of effectiveness, WOMAC and mean QALY (and the scores on the different EQ-5D-5L attributes, such as pain/discomfort), using the general analytic procedures and time points described above for primary and secondary outcomes. We will calculate the incremental cost effectiveness ratio (ICER) of STEP-KOA compared to the AE control group, separately for WOMAC and QALYs. The ICER will be calculated as the difference in the average total cost per participant STEP-KOA and AE, divided by the difference in the average effectiveness per participant between STEP-KOA and AE. Bootstrapping of estimates, multiple imputation for missing EuroQoL values, and sensitivity analyses will all be conducted to ensure robustness of our results.

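### Joint replacement has no stated route into the ICER's cost side, and the QALY ICER may count health gain after surgery without its cost

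*Combined protocol and SAP*

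**What the plan says.** Section 9.0 defines the numerator: "The ICER will be calculated as the difference in the average total cost per participant STEP-KOA and AE". It places the comparison "at the 9-month follow-up point" and describes the approach as "consistent with using the VHA perspective and comparing total aggregated costs across the two study arms".

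Section 7.11 lists what goes into that cost:

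- **Intervention cost.** Labor and equipment for the three Steps are micro-costed and averaged over the STEP-KOA arm.
- **VA utilization.** The paragraph opens with its rationale: "The intervention may affect primary care and specialist outpatient visits for OA and outpatient pain medication use". For VA visits and pain medication, "we will utilize the outpatient extract and pharmacy data extracts". The care total is the "total costs of OA-related outpatient care".
- **Non-VA care.** "We will also include fee basis OA-related outpatient care and costs of the same categories".

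Section 7.10 compares the proportion having joint replacement between arms, "since receipt of total joint replacement is also an important OA outcome". It also takes these participants out of the WOMAC analyses because the operation usually brings a very large improvement. Section 7.11 names two effectiveness measures for the ICERs, WOMAC and EQ-5D-5L QALYs. The exclusion in 7.10 mentions only the first.

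**The concern.** A VHA reader would take an average total cost from the VHA perspective to include a joint replacement that the VHA paid for. As written, the numerator is intervention cost plus OA outpatient and pharmacy cost. The trial will know which arm had more surgery, but the plan does not say that this difference reaches the cost comparison.

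The treatment of surgical participants also differs by measure. In the QALY ICER, nothing removes them from the effect, so better health after surgery can be counted while the surgery costs nothing. In the WOMAC ICER, they leave the effect, but no rule says whether their outpatient, drug and intervention costs leave too. Either ratio could then rest on a cost and an effect that do not match.

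**Working it through.** **1. Trace the surgery through the sections.**

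| Quantity | Is joint replacement included? | Source |
|---|---|---|
| Proportion by arm | Yes | 7.10 |
| WOMAC effect | No, participants removed | 7.10 |
| QALY effect | No exclusion stated | 7.10, 7.11, 9.0 |
| VA cost | Outpatient and pharmacy extracts only | 7.11 |
| Fee basis cost | Outpatient only, same categories | 7.11 |
| Definition of total cost | Components not listed | 9.0 |

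Section 9.0 says the effectiveness measures follow the general procedures for the trial outcomes. That does not settle whether the WOMAC exclusion carries over to QALYs.

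**2. Inputs for size.** The documents give no surgery rate, unit cost or ICER, so there is no cost figure of the plan's to reproduce. Only the arm sizes come from the plan: 230 and 115 (section 8.5). As a check on those, with SD 17.5, difference 5.8, correlation 0.4, 80% power, two-sided 0.05 and 2:1 allocation:

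- AE completers = 1.5 × (17.5 × (1.960 + 0.842) / 5.8)² × (1 − 0.4²) = 107.2 × 0.84 = 90.0
- With 20% attrition: 90.0 / 0.8 = 112.5 in AE, and 3 × 112.5 = about 338 in total, within 3% of the planned 345.

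The assumed inputs are a 9-month surgery rate p of 2% to 6% and a cost per surgery C of $15,000 to $35,000.

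**3. Expected events.** 0.02 × 345 = about 7, and 0.06 × 345 = about 21.

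**4. Shift in the cost difference.** Shift = C × (difference in rates). For a 2-point difference: 0.02 × 15,000 = $300, and 0.02 × 35,000 = $700 per participant. The sign depends on which arm has more surgery. With equal rates the shift is zero.

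**5. Standard error from surgery cost.** With a fixed cost per surgery, a common rate p in both arms and no attrition, SE = C × √(p(1 − p)) × √(1/230 + 1/115), where the last factor is 0.1142.

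| p | C | SE | Shift for 2 points | Shift / SE |
|---|---|---|---|---|
| 2% | $15,000 | $240 | $300 | 1.25 |
| 2% | $35,000 | $560 | $700 | 1.25 |
| 6% | $15,000 | $407 | $300 | 0.74 |
| 6% | $35,000 | $949 | $700 | 0.74 |

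**6. Leverage of one event.** One AE surgery moves that arm's mean cost by 15,000/115 = $130 to 35,000/115 = $304. One STEP-KOA surgery moves its arm's mean by 15,000/230 = $65 to 35,000/230 = $152.

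**The case against.** The restriction has a rationale. The plan costs the resources it expects the intervention to change, and section 7.11 says which these are. Section 3.0 excludes people with surgery planned in the next 9 months, which matches the horizon of the ICER, so events should be few. In its sentence, the reference to total aggregated costs is partly a contrast with costing by Step. Any imbalance in surgery would be visible, because proportions are reported by arm, and section 9.0 promises sensitivity analyses. Surgery costs would also add noise: the illustrated shift is only 0.74 to 1.25 of its own standard error.

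Most of this stands, and it keeps the point small. It does not remove the mismatch. The same sentence of 9.0 claims the VHA perspective, the numerator is separately called average total cost, and the promised sensitivity analyses are not specified. The entry exclusion covers planned surgery, yet 7.10 still provides for surgery during the study. The noise argument supports showing both versions; it does not justify calling the narrower one total cost.

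A reader might infer that the cost side holds only outpatient care and pharmacy. It does not, since intervention labor and equipment are micro-costed as well. A reader might also infer that the plan rules surgery costs out. It does not say so: it names no source for them, and outpatient visits around an operation could still be captured. That the operation itself falls outside the outpatient extract is an inference from the sources named.

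Simply adding surgery cost everywhere would be wrong too. In a WOMAC ICER whose effect omits these participants, it would create a new mismatch.

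**Conclusion.** The point holds as a gap between the label and the content of the cost total, together with an undefined treatment of surgical participants in the two ICERs. The QALY ICER is the more exposed, because it can take the benefit of surgery without the cost.

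A reader might go further and conclude that the ICER will be materially biased. The documents do not support that: they give no surgery rates and no unit costs, few events are expected over 9 months, and equal rates cancel. The $300-700 shift and the standard error of about $240-950 rest wholly on assumed rates of 2-6%, assumed costs of $15,000-35,000 and an assumed 2-point difference. They show only that a few events could matter with 115 participants in the smaller arm. The effect on the ratio itself cannot be computed without the effect difference. This is a low-severity point worth fixing because the fix is cheap.

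**What to change.** - For participants recorded as having joint replacement, extract VA and fee basis inpatient and surgical costs through 9 months.
- Report the QALY ICER with and without these costs, keeping the same participants on the cost and effect sides.
- For the WOMAC ICER, use one participant set for cost and effect. If surgical participants stay out of the effect, take their costs out too, and say that the ratio then describes participants without surgery.
- In section 9.0, list the components of total cost. Label the version without surgery costs as intervention plus OA outpatient and pharmacy cost, not as total VHA cost.

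The cost is one small extract (about 7 to 21 participants under the assumed rates), a few sentences of text, and a noisier estimate when surgery is included. Interventions, sample size and the primary analysis are unaffected.
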